### 9.2.2. Study Period

The *study period* ranges from first authorization date of upadacitinib for the treatment of AD in Denmark and Sweden (23 August 2021) until 31 December 2031.

Individuals initiating one of the treatments under study will be included through the whole *study period*. To allow for at least 5 years follow-up time for malignancy excluding NMSC and NMSC, for these outcomes the population will be restricted to individuals included up until 31 December 2026.

### 9.2.3. Follow-Up

Each individual will be followed specifically for each outcome of interest, from the *index date* to the earliest occurrence of the specific outcome of interest, end of the study period, emigration, death or initiation of any other JAK inhibitor.

## 9.3. Variables

### 9.3.1. Exposure

Exposure will be based on dispensed prescriptions/administrations of either upadacitinib or other select systemic AD treatments. Three exposure definitions will be used, an intention to treat (ITT), a modified ITT with censor at switch, and a time-varying exposure as described below.

#### *ITT exposure definition*

With the ITT exposure definition, individuals will be considered exposed to the first eligible treatment received, from *index date* until the *end of follow-up*. Individuals will only contribute person-time to one treatment.

#### *Modified ITT exposure definition*

[figure not shown]
With the modified ITT exposure definition, individuals will be considered exposed to the first eligible treatment received, from *index date* until *end of follow-up* but in addition censored at treatment switch. Individuals will only contribute person-time to one treatment.

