To reduce inflammation in the skin, either pimecrolimus or tacrolimus can be used for topical treatment. They are calcineurin inhibitors that affect inflammatory dendritic epidermal cells and are recommended as second line treatment due to safety reasons [2]. When using anti-inflammatory treatments, combined therapy with emollients should be used. In rare instances oral corticosteroids may be used for the treatment of exacerbation of AD [2]. For very severe cases of AD, cyclosporin A may be used [2]; however, there are side effects including renal toxicity that may lead to hypertension and renal impairment. Another drug sometimes used for severe AD is azathioprine. However, side effects include myelo-suppression, hepatotoxicity, gastrointestinal disturbances, increased risk of infections and possibly skin cancer.

More recently, subcutaneous, oral and topic biologic drugs have been introduced for clinical use in AD. In 2017, the monoclonal antibody dupilumab was approved in the US and EU for adults with moderate to severe AD. Dupilumab binds to interleukin-4 (IL-4) receptors which are involved in signaling pathways relevant for the development of AD [16]. Abrocitinib was approved for adults with moderate to severe AD in the EU in December 2021. Moreover, additional drugs may come to be introduced to the market (e.g., crisaborole, nemolizumab) [17, 18].

Upadacitinib is an oral selective and reversible inhibitor of JAK1. Upadacitinib doses of 15 mg and 30 mg are approved to be used in the EU for treatment of adults with moderate to severe AD. Upadacitinib 15 mg is approved to be used in the EU for treatment of adolescents with moderate to severe AD who weigh 30 kg or over. Following the procedure under Article 20 of Regulation (EC) No 726/2004 (concluded 10 March 2023), upadacitinib recommended use and doses have been changed. Upadacitinib 15 mg is approved to be used in the EU for treatment of elderly patients  $\geq 65$  years of age or patients with risk factors for malignancy, major adverse cardiovascular events (MACE) or venous thromboembolic events (VTEs). In addition, upadacitinib should only be used, if no suitable alternatives are available, in patients 65 years of age or older, in patients with history of atherosclerotic cardiovascular disease or other cardiovascular risk factors and in patients with malignancy risk factors.

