## 9.7. Data Analysis

The labeling updates due to the Article 20 procedure pose distinct challenges for the long-term safety study in atopic dermatitis (AD). First, patients treated with upadacitinib will be expected to differ from other select systemic treatments in baseline risk factors for major cardiovascular events (MACE), malignancy and/or venous thromboembolic events (VTE), based on the updated section 4.4 (Special warnings and precautions for use) of the RINVOQ Summary of Product Characteristics (SmPC). Second, high risk patients treated with upadacitinib will likely be those with “no suitable treatment alternatives” and be more likely to have failed other therapies, not responded to the lower dose of upadacitinib, and have higher disease burden. Third, the anticipated lower incidence of safety outcomes in low-risk patients raises feasibility concerns, particularly as these relate to precision requirements for comparative analyses.

To address these challenges, assessment of comparability of users of upadacitinib and other select systemic treatments for AD will be conducted through in-depth assessments of treatment pattern utilization and patient disposition at baseline (see Section 9.7.1).

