### 9.7.2. Comparative Analysis

[REDACTED] analyses will be performed to compare upadacitinib and comparator treatments in the final report.

Comparisons of rates of safety outcomes between upadacitinib and comparator cohorts will be made with Cox proportional hazard regression models using appropriate strategies such as IPTW, PS matching/ stratification/ adjustments or others to achieve comparable balance across cohorts.

[Table 7](#) below specifies the exposure definitions that will be used as time at risk for each outcome.

With the ITT exposure definition, individuals will be considered exposed to the first eligible treatment received until the end of follow-up while with the modified ITT individuals will be considered exposed to the first eligible treatment received and censored at treatment switching. With both ITT and modified ITT, Cox proportional hazards regression models with treatment group (upadacitinib, comparator) as exposure will be performed. For malignancy, exposure time and time to event will start to be counted from the lag-time (for main analysis 12 months) from index date.

With the time-varying exposure definition individuals may change exposure status when starting different treatments, and thus the treatment covariate is time-varying. Cox proportional hazards regression models with treatment group (upadacitinib, comparator, unexposed time, concomitant use/switch) as covariate will be performed. The time scale in the models will be time since start of the treatment group, i.e., time since beginning of the exposure to the specific treatment group (upadacitinib, comparator, unexposed time, concomitant use/switch).

The hazard ratio (HR) and 95% confidence interval (CI) will be reported from the Cox models. Kaplan-Meier curves for all outcomes will also be reported. In addition, 5-years overall survival rate will be presented for malignancy excluding NMSC, NMSC, MACE and all-cause mortality as well as 5-years event-free survival rates for malignancy excluding NMSC, NMSC and MACE.

Analyses will be performed based on pooled individual data, unless legal barriers towards transfer of individual data make it impossible, in which case meta-analyses of aggregated data will be performed instead. Methods for meta-analysis will be described in the SAP and the barriers for data pooling will be assessed in connection with the interim report.

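### The modified ITT analysis censors at treatment switch but names no method for switching that depends on risk arising after the index date

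*Protocol*

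**What the plan says.** Section 9.3.1 sets three exposure definitions: ITT, modified ITT and time-varying. Modified ITT follows the first eligible treatment from the index date to the end of follow-up, "but in addition censored at treatment switch". Section 9.7.2 repeats that patients are "considered exposed to the first eligible treatment received and censored at treatment switching" and states the model: "With both ITT and modified ITT, Cox proportional hazards regression models with treatment group (upadacitinib, comparator) as exposure will be performed". Confounding is to be handled "using appropriate strategies such as IPTW, PS matching/ stratification/ adjustments or others to achieve comparable balance across cohorts".

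Section 9.3.2 names modified ITT, alongside ITT, in the risk window for malignancy excluding NMSC and for NMSC. The risk window for all other outcomes names only ITT and time-varying exposure. Table 7, which assigns definitions to outcomes, has no legible entries in the public text; that is not a fault of the plan.

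Section 7 (and the abstract) gives the label position after the Article 20 procedure: "upadacitinib should only be used, if no suitable alternatives are available, in patients 65 years of age or older", and likewise "in patients with history of atherosclerotic cardiovascular disease or other cardiovascular risk factors and in patients with malignancy risk factors". No such restriction is quoted for the comparator drugs.

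The sensitivity analyses named in 9.7.2.1 concern prior systemic treatment and the malignancy lag. Section 9.9 does not mention switching or informative censoring.

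**The concern.** A Cox model that stops follow-up at a switch is valid only if, conditional on the covariates used, patients who switch have the same later outcome risk as those who do not. Weighting or matching on a baseline propensity score makes the cohorts alike at the index date. It does nothing about risk that changes afterwards and also drives switching.

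The protocol gives a reason to doubt the assumption. The study period runs from August 2021 to December 2031, so some patients will pass 65 or acquire cardiovascular or malignancy risk factors during follow-up, and others who started before March 2023 will meet the new restriction partway through. The restriction concerns one arm of the comparison. If it affects who switches, the arms can lose high-risk person-time at different rates, and the modified ITT hazard ratio then partly reflects that selection.

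**Working it through.** The protocol states no figure on this point and gives no switch rates, so there is nothing to reproduce. The check asks which way, and how far, a true ratio of 1.00 could move.

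**Model.** There are two risk states, low (L) and high (H), the drug has no effect, and follow-up lasts 5 years. With event rate λ in L and kλ in H, rate q of moving from L to H, and switch (censoring) rates s_L and s_H:

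- dL/dt = −(q + λ + s_L)·L
- dH/dt = q·L − (kλ + s_H)·H
- observed rate = ∫(λL + kλH)dt ÷ ∫(L + H)dt
- observed ratio = upadacitinib rate ÷ comparator rate

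**Inputs, all assumed.** λ = 0.004 per year; k = 2 or 4; q = 0.02 or 0.05 per year; 10% in H at index in both arms; switch rate 0.15 per year everywhere except for high-risk users as shown.

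| High-risk switch rate per year, upadacitinib vs comparator | k=2, q=0.02 | k=2, q=0.05 | k=4, q=0.02 | k=4, q=0.05 |
|---|---|---|---|---|
| 0.15 vs 0.15 (unrelated to risk) | 1.00 | 1.00 | 1.00 | 1.00 |
| 0.4 vs 0.4 (same dependence in both arms) | 1.00 | 1.00 | 1.00 | 1.00 |
| 0.4 vs 0.15 (upadacitinib switches more) | 0.96 | 0.95 | 0.91 | 0.89 |
| 0.8 vs 0.15 (much more) | 0.93 | 0.91 | 0.83 | 0.80 |
| 0.05 vs 0.15 (upadacitinib switches less) | 1.02 | 1.03 | 1.06 | 1.06 |

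The ratio moves only when the dependence of switching on risk differs between arms, and the sign of that difference sets the direction. With equal dependence (second row) the ratio is unharmed, but the upadacitinib rate itself is 0.87 to 0.96 of its value without censoring at switch.

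**A simpler one-sided scenario.** Let h be the share of time spent at newly raised risk, k the hazard factor and s the fraction of that time censored in the upadacitinib arm only:

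ratio = [((1−h) + h(1−s)k) ÷ ((1−h) + h(1−s))] ÷ [(1−h) + hk]

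With h = 0.10, k = 4, s = 0.7: (0.90 + 0.12) ÷ (0.90 + 0.03) = 1.02 ÷ 0.93 = 1.097, and 1.097 ÷ 1.30 = 0.84. Over h = 0.05 to 0.15, k = 3 to 5 and s = 0.5 to 0.7, the ratio runs from 0.96 to 0.75. This formula puts all the extra switching in one arm, so it can only give values below 1. It is one assumed scenario and does not show direction.

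**Limits of the illustration.** These are crude rate ratios, not Cox estimates. The table also includes patients already at high risk at index; direct adjustment for that risk in the outcome model would remove part of the distortion.

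**The case against.** Five arguments on the other side carry weight.

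- **The label is conditional.** It limits use in certain patients to those with no suitable alternative. It does not say to switch when risk rises during treatment. This stands.
- **The protocol's own expectation can point the other way.** Section 9.7 says "high risk patients treated with upadacitinib will likely be those with" no suitable alternative, and that they will "be more likely to have failed other therapies, not responded to the lower dose of upadacitinib, and have higher disease burden". Such patients have less to switch to. This stands as a reason not to assert a direction. It describes patients already at high risk when treated, though, and 9.2.1 requires prior systemic treatment only of the comparator cohorts, so upadacitinib starters who become high risk later may still have options.
- **Comparators have risk-related reasons to switch too.** Section 7 lists renal toxicity and hypertension with ciclosporin, and possible skin cancer with azathioprine. This stands.
- **Only a switch censors.** A patient who stops upadacitinib and starts nothing else remains in follow-up. Passing 65 is also determined by age at index, which the propensity model can use. Both points shrink the problem; neither covers diagnoses made after index.
- **ITT is planned, and detail belongs in the statistical analysis plan.** For malignancy and NMSC, ITT stands beside modified ITT and does not censor at a switch between study treatments. It is a partial check: it answers a different question, and under 9.2.3 it still censors when another JAK inhibitor is started. Section 9.7.2.1 defers sensitivity-analysis detail to the statistical analysis plan, which is not at hand and may already contain a correction.

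**Conclusion.** The protocol fixes a censoring rule and a model that together need switching to be independent of outcome risk given baseline covariates, and it also quotes a restriction on one arm that gives a reason why this may fail. The legible text does not state the assumption, define a switch for modified ITT or name a check. This is a worthwhile and inexpensive improvement; it does not show that the analysis is wrong.

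A reader might infer that upadacitinib loses its highest-risk time and that the hazard ratio is therefore biased towards safety. The documents do not support that. They give no switch rates, the label text is not an instruction to switch, and the assumed scenarios fall on both sides of 1 (0.80 to 1.06 in the table). The 0.84 figure is correct arithmetic on one-sided assumptions.

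A reader might also extend the point to MACE, VTE or death. That is unconfirmed: modified ITT is legibly assigned only to malignancy and NMSC. The point applies to any further outcome that Table 7 assigns to it.

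**What to change.** In section 9.7.2, or in the statistical analysis plan with a reference from there:

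1. State the independent-censoring assumption for modified ITT and define switch for it, including whether adding a second study treatment counts.
2. Tabulate switches by cohort and by newly recorded risk factors.
3. Beside the unweighted modified ITT result, report one weighted by the inverse probability of remaining unswitched. Estimate the weights separately by arm from time-updated register covariates: attained age, new cardiovascular or cancer-risk diagnoses, newly dispensed cardiovascular drugs, recent hospitalisation and AD contacts. For the malignancy outcomes, accumulate the weights from the index date rather than from the end of the lag, because switches during the lag also determine who remains.
4. Report the ITT result for the same outcomes alongside.
5. Name informative censoring at switch in section 9.9.

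The data come from registers the study already links. The cost is additional analysis work and somewhat wider intervals for the weighted estimate. The weights remove only the part of the bias that the recorded covariates explain.

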#### *Time-varying exposure definition*

For the time-varying exposure definition, treatment episodes will be constructed as described in the following steps and illustrated in [Figure 1](#):

1. All dispensed prescriptions/administrations of upadacitinib and comparator treatment within the *study period* are identified.
2. The duration of each dispensed prescription/administration of upadacitinib and the systemic comparator treatments will be calculated using the assumed daily dosage, i.e., the duration of each dispensed prescription/administration in days equals the total amount of treatment received divided by the assumed daily dosage.
3. If the next dispensed prescription/administration of the same treatment is before the calculated end date of the current dispensed prescription/administration the overlap will be ignored, assuming that the amount previously received would be completely used.
4. If the gap between the end date of the current dispensed prescription/administration and the start date of the next dispensed prescription/administration with the same treatment is less than or equal to 30 days, then the treatments will be considered within the same *treatment episode* and the gap will be considered exposed time.
5. After the duration of each treatment episode is calculated, a period of 30 days (equal to the allowed gap) will be added at the end of a *treatment episode*.

6. If a dispensed prescription/administration of another study treatment starts at the same date or during the *treatment episode* of one of the study treatments, the overlapping days between treatments will be categorized as “concomitant use/switch”.
7. Periods of time without any of the studied treatments will be categorized as “unexposed time”.

With the time-varying exposure definition individuals may change exposure status during *follow-up* depending on the treatment received, hence individuals will contribute person-time to several treatments.

### 9.3.2. Outcomes

The outcomes will be first event of:

- Malignancy (excluding NMSC), including malignancy by type
- NMSC
- MACE
- VTE

- Serious (in-patient) infections (incl. OI)
- HZ
- EH/KVE
- Active TB
- GI perforations
- DILI
- Fractures
- All-cause mortality

Incident malignancies will be identified via the linked national cancer registers and the national patient registers in each country. The other outcomes will be captured through inpatient and specialist outpatient diagnoses, as reflected in the national patient registers, in each country. Details on the coding, definitions, history exclusion look-back periods and source of the outcomes are listed in Annex 3. Additional Information, [Table 3.3](#).

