As with other JAK inhibitors also marketed in Europe, important potential safety risks have been identified for the JAK class. Such safety risks include malignancy, serious and opportunistic

infections including tuberculosis (TB) and herpes zoster (HZ), fetal malformation (pregnancy risk), MACE, VTE, gastrointestinal (GI) perforation and fractures.

From a clinical and safety perspective, it is important to gain knowledge of these and other safety concerns for upadacitinib, and if feasible, to provide comparisons with other relevant treatment alternatives for AD. To achieve this, data from real-world settings are needed [19].

This long-term safety study will therefore be conducted to assess the long-term safety of upadacitinib use in patients with AD in a real-world setting.

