### The primary objectives are:

To assess comparability across upadacitinib and other select systemic treatments for AD through in-depth assessments of treatment pattern and patient disposition at baseline.

To describe the incidence of the following safety outcomes in adolescent and adult individuals with AD treated with upadacitinib:

- malignancy (excluding NMSC), including malignancy by type
- NMSC
- MACE
- VTE
- serious (in-patient) infections (incl. OI)
- HZ
- EH/ KVE
- active TB
- GI perforation
- DILI
- fractures
- all-cause mortality

If a suitable comparator is identified: to describe and compare (when feasible) the incidence of the above safety outcomes in adolescent and adult individuals with AD treated with upadacitinib, relative to those treated with other select systemic AD treatments.

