#### 9.4. Data Sources

Data from the national patient registers, the national prescribed drug registers, the national cancer registers, the cause of death registers and the population-based registers in Denmark and Sweden will be used. In addition, the Danish Hospital Medicines Register (if available at the time of data extraction) and the Danish Educational and Socioeconomic Registries will be used.

The assignment of unique personal identification numbers (PIN) to all Danish and Swedish residents at birth or upon immigration makes it possible to cross-link data between the national registers within each country. The PIN is kept unchanged throughout life, so individuals can be followed-up throughout their lifetime, except for migrants. The registers are updated on a yearly basis with up to two years production time before released to research, depending on content. The registers contain the following information:

- From the population-based registers and the Danish Educational and Socioeconomic Registries information on demographic variables, migration and socioeconomic factors will be obtained.
- The national patient registers contain information on all hospitalizations and outpatient visits to specialist care, including primary and secondary diagnoses recorded at discharge. Diagnoses of AD, medical history, comorbidities, and outcomes are recorded according to the International Classification of Diseases, revision 10 (ICD-10).
- The national cancer registers contain information on all incident cancer diagnoses (morphologically verified). In addition, information about cancer diagnoses might also be obtained from the national patient registers.
- The date and cause of death will be obtained from the cause of death registers. In Denmark civil registration system will be used for identifying date of death.

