- The prescribed drug registers include data on the formulations and date of all dispensed prescriptions. Drugs are categorized according to the WHO Anatomical Therapeutic Chemical classification system (ATC codes) [20]. Main exposure in Sweden will be defined based on dispensed prescriptions from the prescribed drug register for all treatments, while in Denmark exposure will be captured by treatment codes in the patient register and dispensed prescriptions in the prescribed drug register. When captured by treatment codes in the patient register information about dose, strength, amount dispensed will not be available. If available, Danish Hospital Medicines Registry might be used in addition. This data source is currently undergoing testing and may become available in 2023.
- The contagious disease register, since 1971, provides events reported according to the Swedish Communicable Diseases Act and the communicable diseases ordinance on diseases e.g. TB that have mandatory reporting in Sweden.

The above-mentioned national registers hold data on almost all inhabitants in Sweden (population 10.2 million) and Denmark (population 5.8 million). The coverage and quality of the Danish and Swedish Registers have been well established in the literature [21]. Due to the breadth of capture of clinical outcomes across providers as well as “cradle to grave” longitudinal coverage, these registries have been successfully utilized for numerous post-marketing safety studies.

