### **9.9. Limitations of the Research Methods**

Some information is not collected in national registers including score-based AD disease severity and patient reported outcomes. Individuals only diagnosed with AD in primary care will not be included, and diagnostic information for conditions only seen in primary care will also be missing. The ability to assess and address bias will be detailed in the selection of comparison treatments and in the analytic approach. Confounders will be identified and adjusted for and the potential for residual confounding will be considered, and any relevant sensitivity analyses will be proposed. The role of unmeasured confounding and its influence on the study results will be discussed in the reports.

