**Table 3.3. Outcomes**

Diagnosis Codes (ICD-O-3 and ICD-10)	Register	History exclusion look-back period	Description
Malignancies excluding NMSC			
[REDACTED]	Cancer/Patient	5 years	
Non-melanoma skin cancer (NMSC)			
[REDACTED]	Cancer/Patient	5 years	
MACE (non-fatal MI, non-fatal stroke, CV death)			
[REDACTED]	Patient, Cause of Death		
Serious infections (any hospital-treated infections, including opportunistic infections)			
[REDACTED]	Patient	1 year	Respiratory tract infections. In-patient only
[REDACTED]	Patient		Infections of the gastrointestinal tract* In-patient only
[REDACTED]	Patient		Urinary tract infection
[REDACTED]	Patient		Infections of the skin and subcutaneous tissue In-patient only
[REDACTED]	Patient		Other infections In-patient only
Venous thromboembolic event (VTE)			
[REDACTED]	Patient	5 years	
Herpes zoster (HZ)			
[REDACTED]	Patient	1 year	
Eczema herpeticum (EH)/Kaposi's varicelliform eruption (KVE)			
[REDACTED]	Patient	1 years	
Active tuberculosis (TB)			

Diagnosis Codes (ICD-O-3 and ICD-10)	Register	History exclusion look-back period	Description
[REDACTED]	Patient	5 years	J04AK05 (bedaquiline)J04AK01 (pyrazinamide)J04AK02 (ethambutol)
Gastrointestinal (GI) perforations			
[REDACTED]	Patient	5 years	
Drug-induced liver injury (DILI)			
[REDACTED]	Patient	5 years	Toxic liver disease
All-cause mortality			
[REDACTED]	Cause of Death		All deaths in Cause of Death Register
Fractures			
[REDACTED]	Patient	5 years

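### Herpes zoster is ascertained only from hospital and specialist diagnoses, so the absolute HZ incidence the study reports will be too low by an unknown factor

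*Protocol*

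**What the plan says.** The primary objectives (Protocol section 8) include this one: "To describe the incidence of the following safety outcomes in adolescent and adult individuals with AD treated with upadacitinib". HZ is in the list that follows, separate from serious in-patient infections. Section 7 also names HZ among the safety risks of the JAK class.

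Section 9.3.2 takes malignancies from the cancer and patient registers and then says of the rest: "The other outcomes will be captured through inpatient and specialist outpatient diagnoses, as reflected in the national patient registers". In Table 3.3 the HZ row shows the patient register and a one-year history look-back. Its code cell is redacted. Unlike most of the serious-infection rows, it has no in-patient restriction.

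Section 9.4 describes that register: "The national patient registers contain information on all hospitalizations and outpatient visits to specialist care". Section 9.9 draws the consequence in general terms: "diagnostic information for conditions only seen in primary care will also be missing". It does not mention HZ, a direction of error or a remedy. Section 9.7.3 reads the absence of a record as absence of the condition. In the ENCePP checklist (Annex 2), validity of outcome measurement (item 6.3) is marked not applicable, and control of outcome misclassification (item 10.6) is marked no.

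Section 9.4 also describes a second linked source: "The prescribed drug registers include data on the formulations and date of all dispensed prescriptions". No use of it for HZ is visible.

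**The concern.** The objective and the outcome list speak of HZ without qualification, whereas the stated source can deliver only HZ that reaches a hospital or a specialist clinic. Any episode treated solely in primary care is counted as event-free person-time. The resulting rate would be read as the incidence of HZ under upadacitinib, for a risk the protocol itself singles out, although part of that incidence cannot be seen by design. The lost events also cost precision. In addition, capture depends on how often a person sees a specialist, so a comparison between cohorts is safe only if that contact is similar.

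**Working it through.** There is no plan figure to reproduce. Section 9.5 is redacted, and no HZ rate, event count, target effect or power is visible.

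**Inputs from the Protocol.** Source of HZ: hospital and specialist-clinic diagnoses (section 9.3.2, Table 3.3). Register coverage: no primary care (sections 9.4 and 9.9). No record means no event (section 9.7.3). Upadacitinib users are expected to have more treatment failure and higher disease burden (section 9.7).

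**Assumed input.** Sensitivity of capture, *s*, is the share of HZ episodes that receive a hospital or specialist diagnosis. The documents give no value, so a range of 0.2 to 0.9 is used. Events are taken as rare and specificity as 1.

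**Step 1: absolute rate and precision.** Reported rate = *s* × true rate. The number of events falls by the factor *s*, so the width of a log-scale confidence interval grows by 1/√*s*.

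| *s* (assumed) | Share of true rate reported | CI width relative to full capture |
|---|---|---|
| 0.2 | 20% | 1/√0.2 = 2.24 |
| 0.3 | 30% | 1.83 |
| 0.5 | 50% | 1.41 |
| 0.7 | 70% | 1.20 |
| 0.9 | 90% | 1.05 |

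The rate is understated for every *s* below 1. Only the amount depends on the assumption.

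**Step 2: hazard ratio.** Reported HR = true HR × *s*₁/*s*₀, where *s*₁ is capture in the upadacitinib cohort and *s*₀ capture in the comparator cohort. Equal capture leaves the HR unbiased: 0.30/0.30 = 1.00. With a true HR of 1.0 and unequal capture (all values assumed):

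- 0.36/0.30 gives 1.20
- 0.45/0.30 gives 1.50
- 0.30/0.40 gives 0.75

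The bias can therefore go either way.

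**Step 3: power, as illustration only.** Assume HR 1.5, two-sided 5%, 1:1 cohorts and 80% power. Schoenfeld's formula gives 4 × (1.960 + 0.842)² / (ln 1.5)² = 191 events. At *s* = 0.5 about 96 events remain and power is 51%. At *s* = 0.3 about 57 remain and power is 33.5%.

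**The case against.** *The limitation is disclosed.* Section 9.3.2 is open about the source, and section 9.9 names the gap. That is true, and the plan does not contradict itself. But the disclosure is generic, and it does not correct a primary-objective rate or tell a reader which way the HZ figure errs.

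*Definitions are left to the SAP.* Annex 3 says its tables are not final, and section 9.7.2.1 leaves the detail of sensitivity analyses to the SAP. This stands for codes and algorithms. The restriction of the source, however, is set in the body of the protocol, so it is not merely a gap awaiting the SAP.

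*Drug codes may already be used.* The HZ code cell is redacted, and the active TB row lists drug codes although its register column also shows only the patient register. The register column alone is therefore not proof. Section 9.3.2 nevertheless speaks of diagnoses, and no drug source is visible for HZ.

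*Capture may be good in this cohort.* Section 9.2.1 requires an AD diagnosis in the patient register and systemic treatment within 12 months of it, so these people have had specialist contact. This is a fair reason to include values of *s* as high as 0.9.

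*A reader might infer spuriously raised HZ rates on treatment compared with off treatment.* Under the time-varying definition, section 9.7.2 states: "Cox proportional hazards regression models with treatment group (upadacitinib, comparator, unexposed time, concomitant use/switch) as covariate will be performed". People on a systemic drug may well see specialists more often than during unexposed time. The documents do not support making this the point. The comparative objective concerns upadacitinib against other systemic treatments, not treated against untreated time, and the entries of Table 7 that would show which exposure definition applies to HZ are not visible.

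**Conclusion.** The point holds for the absolute rate. As planned, the reported HZ incidence is that of hospital or specialist-diagnosed HZ and lies below the true incidence whenever some zoster is managed only in primary care. Over the assumed range of *s* from 0.2 to 0.9, the shortfall runs from 80% down to 10% of the true rate, and the interval is between 2.24 and 1.05 times as wide.

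Three stronger readings should be resisted. A reader might infer that most HZ events are lost or that the rate is understated several-fold. That follows only if *s* is below 0.5, and nothing in the documents fixes *s*. A reader might infer that the protocol states a wrong HZ incidence, but no HZ rate is visible in it. A reader might infer that the HR against active comparators is biased. That requires unequal capture between cohorts. Section 9.7 makes this plausible through the expected difference in disease burden, but does not show it.

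The change is worth making because it concerns a primary objective and a named class risk, and the data for a check are already linked.

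**What to change.** 1. Label the Table 3.3 endpoint *hospital or specialist-diagnosed HZ* and carry that label into the reports.
2. In section 9.9, name HZ, state that its absolute incidence will be understated, and state that the HR is affected only if specialist capture differs between cohorts.
3. Add one sensitivity definition from the prescribed drug registers: the first HZ diagnosis or the first dispensing of a systemic antiviral in a pre-specified zoster-treatment pack or quantity. Keep the same one-year look-back. Exclude dispensings close in time to a herpes simplex or EH/KVE diagnosis, and persons with repeated or long-term antiviral dispensings.
4. Report incidence and, where comparisons are made, the HR under both definitions.

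The cost is a change of label, a few sentences, and one additional outcome algorithm on registers already in the linkage. The downside is lower specificity. The simplex and EH/KVE exclusions rely on the same specialist diagnoses, so simplex treated in primary care cannot be fully removed. Section 7 notes a raised herpes simplex risk in AD, and such false positives may differ by treatment. The report should say so, and the second definition should stand beside the diagnosis-based endpoint without replacing it.
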